5.3 Duration of follow-up

Patients will be followed for 4 weeks after removal from study and patient records will be reviewed until death or 2 years from enrollment (whichever comes first) to assess progression and survival. Patients removed from study for unacceptable adverse event(s) will be followed until resolution or stabilization of the adverse event.

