TITLE: INFLUENZA VACCINATION IN PLASMA CELL DYSCRASIAS

Coordinating Center: Winship Cancer Institute of Emory University

Winship PI: [name] MD MPH

Laboratory investigator: [name] MBBS

Sanofi: Fluzone HD

Commercial Agent: Prevnar 13 (PCV 13)

Statistician: [name] Winship BBISR

Protocol / Date:

Initial / 7-May-2019
V 1.1 / 22-May-2019
V 1.2 / 13-Jul-2019
V 1.3 / 31-Oct-2019
V 1.31 / 13-Nov-2019
V 2.0 / 9-Mar-2020
V 2.1 / 7-Apr-2020
V 2.2 / 3-Jul-2020
V 2.3 / 20-Jul-2020
V 2.4 / 14-Sep-2020

CTCAE version: 5.0

[figure not shown]
Total consented patients: 175 total
50 patients (2019-2020) of which 23 were evaluable
125 patients (2020-2021)

Text color legend

Blue text
Blue text

Instructions and detailed for correlative science for laboratory #1
Instructions and detailed for correlative science for laboratory #2

SCHEMA

This is a phase IV randomized trial of 148 evaluable patients with a plasma cell disorder to be enrolled as early as possible in the influenza season through 15-Dec.

Fluzone HD refers to TIV formulation for 2019-2020 influenza season and QIV formulation for 2020-2021 season.

After eligibility is confirmed, patients will be randomized 1:1 to either an experimental arm where each patient receives three injections of Fluzone HD and a control arm where each patient receives one injection of Fluzone HD.

All patients receive Prevnar at week 5 if they have not received either PCV13 or PPSV23 in that calendar year.

STANDARD OF CARE AND RESEARCH INTERVENTIONS

Timing	Week 1	Week 5	Week 9	Week 17	Week 21
Standard of care tests	
 Blood tests Clinic visit 	Prevnar (PCV13)			Myeloma proteins
Research	
 Consent Eligibility Research blood Fluzone HD #1 	Research blood	Fluzone HD #2	Fluzone HD #3	Research blood

Timing	Week 1	Week 5	Week 9	Week 17	Week 21
Standard of care tests	
 Blood tests Clinic visit 	Prevnar (PCV13)			Myeloma proteins
Research	
 Consent Eligibility Research blood Fluzone HD #1 	Research blood			Research blood

Table of Contents

1. PRIMARY HYPOTHESES, OBJECTIVES, AND ENDPOINTS	6
2. EXPLORATORY SCIENTIFIC HYPOTHESES, OBJECTIVES, AND ENDPOINTS	6
3. BACKGROUND	6
3.1 INFLUENZA OVERVIEW	6
3.2 INFLUENZA RISK IN ADULT CANCER PATIENTS	6
3.3 INFLUENZA VACCINATION RESEARCH IN ALLOGENEIC TRANSPLANT PATIENTS.....	7
3.4 MULTIPLE MYELOMA.....	7
3.5 MYELOMA PATIENTS AND INFLUENZA.....	8

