1. PRIMARY HYPOTHESES, OBJECTIVES, AND ENDPOINTS

Clinical		
Hypothesis	Objective	Endpoint
Continuous FluZone HD throughout the flu season will improve hemagglutination inhibition (HAI > 40) as measured at the end of the season compared to those patients that receive FluZone HD once.	Demonstrate an absolute 25% increase in seroprotection, defined as HAI>40 against all strains, at week 21 in the experimental arm compared to the control arm.	HAI will be measured in all patients at baseline, week 5, and week 21 to calculate seroconversion at week 5 and seroprotection at week 21. Seroconversion: Pre-vaccination HAI<10 and a post-vaccination HAI>40 or a pre-vaccination HAI >10 and a \geq 4-fold rise in post-vaccination HAI at week 5.

The above measurables will appear in the results section of www.clinicaltrials.gov at trial completion

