5.2 Duration of therapy

Patient may remain on study until one of the following criteria applies:

- Intercurrent illness that prevents administration of vaccine or follow-up,
- Per physician discretion in the setting of unacceptable adverse event(s), or other medical condition or situation occurs such that continued participation in the study would not be in the best interest of the participant. In patients who are randomized to the experimental arm only, specific adverse events include grade 3 adverse event that occurs without alternative etiology in the 7 days following the first study vaccination

- Patient decides to withdraw from the study, or
- General or specific changes in the patient's condition render the patient unacceptable for further treatment in the judgment of the PI.
- Termination or suspension of the study for safety reasons

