5.4 Criteria for removal from study

Patients will be removed from study when any of the criteria listed in [Duration of therapy](#) applies. The reason for study removal and the date the patient was removed must be documented in the appropriate case report form.

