6.5 Schedule of events

Experimental arm

Assessment	Screening + First visit	Week 5 ^a	Week 9 ^a	Week 17 ^a	Week 21 ^a
Signed informed consent	X				
Vital signs	X				
CBC/d/p ^d	X				
CRP, Serum IG's, LDH	X				
Myeloma proteins ^e	X				X
Blood for research ^f	40 mL	40 mL			40 mL
Fluzone HD	X		X	X	
Prevnar (PCV13)		X			
Record grade \geq 2 adverse events ^g	X		X	X	
Influenza-like illness update ^b		X	X	X	X
PFS and OS ^h					X

Control arm

Assessment	Screening + First Visit	Week 5 ^a	Week 9 ^a	Week 17 ^a	Week 21 ^a
Signed informed consent	X				
Vital signs	X				
CBC/d/p ^d	X				
CRP, Serum IG's, LDH	X				
Myeloma proteins ^e	X				X
Blood for research ^f	40 mL	40 mL			40 mL
Fluzone HD	X				
Prevnar (PCV13)		X			
Record grade \geq 2 adverse events ^g	X				
Influenza-like illness update ^b		X	X	X	X
PFS and OS ^h					X

- a. Assessments on these days can be performed within a \pm 5 day window. Subsequent visits (weeks 5, 9, 17, 21) are based on the actual time of Fluzone HD vaccination, not the pneumonia vaccination.
- b. Involves contact between study personnel and the patient regarding influenza-like illness and SAEs. An in-person visit is not required.
- c. All patients (N=148) will have research blood drawn for correlative science. In both arms, blood will be obtained at baseline, week 5, and week 21. The first 20 patients in each group (n=40 total), split evenly between intervention arm (20 experimental, 20 control), had additional blood drawn 1 week after each Fluzone HD dose (week 2 for control arm and weeks 2, 10, and 18 in the experimental arm) – this was completed 17-Nov-2019.
- d. CBC, differential, and platelets will be performed pre-vaccination.
- e. If not done with results available within 30 days of initial vaccination, a modified myeloma disease assessment requested but not required to include SPEP and free light chains if either were measurable per IMWG criteria in the past. Serum IgD or IgE are requested if a monoclonal IgD or IgE were present in the past. For patients with an IgA monoclonal protein, Hevylite IgA can be used to replace serum immunoglobulins and SPEP.
- f. Peripheral blood samples will be obtained and analyzed as described in correlative science section.

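### Sections 5.2–5.4 do not secure the week-21 HAI once a patient is removed from study, a loss that can differ by arm, and Sections 10.2 and 10.3 use different definitions of evaluable

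*Combined protocol and SAP*

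**What the plan says.** **Removal and follow-up.** Section 5.2 lists the events that end a patient's time on study. Section 5.4 makes them removal criteria: "Patients will be removed from study when any of the criteria listed in" Section 5.2 apply. Section 5.3 states what happens next: "Patients will be followed for 4 weeks after removal from study and patient records will be reviewed until death or 2 years from enrollment". That record review is for progression and survival. Patients removed for an unacceptable adverse event are also followed until it resolves or stabilises.

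**Triggers.** One Section 5.2 criterion is "Intercurrent illness that prevents administration of vaccine or follow-up". Another is a change in condition that would "render the patient unacceptable for further treatment in the judgment of the PI". Under physician discretion there is a named example: "In patients who are randomized to the experimental arm only, specific adverse events include grade 3 adverse event that occurs without alternative etiology". It counts only within 7 days of dose 1. Withdrawal by the patient and general physician discretion apply to both arms.

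**Planned measurement.** Section 1 says "HAI will be measured in all patients at baseline, week 5, and week 21", and the primary objective is seroprotection at week 21. A footnote to Section 6.5 says "In both arms, blood will be obtained at baseline, week 5, and week 21". Neither mentions patients who have been removed.

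**Analysis set.** Section 10.2 calls a patient evaluable after at least one dose if consent is not withdrawn before the first response assessment, whose time point it does not name. It scores a missing assessment as non-response only when the cause is early progression or death. Section 10.3 reports 50 patients enrolled in 2019–2020, of whom 23 are evaluable because 27 missed week 21 owing to COVID19; the title page repeats the 23. Section 10.4.5 names the chi-square test and logistic regression and gives no rule for missing HAI.

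**The concern.** Stopping vaccine and leaving the study are treated as one event. A patient who should receive no further dose can usually still give blood at week 21, and the randomised comparison needs that sample. If removal ends sampling, the primary comparison rests on the patients who stayed.

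The triggers are not symmetric. The named grade 3 example is for the experimental arm only. The criteria about giving vaccine or further treatment bear mainly on that arm, because controls have no Fluzone HD after week 1. They do not bear on it exclusively: "All patients receive Prevnar at week 5 if they have not received either PCV13 or PPSV23 in that calendar year", so a vaccine may still be due in either arm at week 5.

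The second problem concerns who is analysed. If the first response assessment is the week-5 HAI, a dosed, consenting season-1 patient without a week-21 sample is in the Section 10.2 efficacy set but is not evaluable as Section 10.3 uses the word. The trial is meant to support a change in practice (Section 3.5), so its primary set should have one meaning before the data are seen.

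**Working it through.** **1. The plan's own figure.** Inputs from Section 10.3: 0.333 and 0.585, equal arms, alpha 0.05 (taken as two-sided, as in the initial design), power 80%, R-squared 0.1. For logistic regression on a binary covariate (Hsieh formula), with mean rate P = (0.333 + 0.585)/2 = 0.459 and B = 0.5:

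n = [1.960·√(P(1−P)/B) + 0.842·√(0.333·0.667 + 0.585·0.415)]² / [0.252²·(1−B)] = 120.38

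120.38/(1 − 0.1) = 133.76, rounded up to 134, as stated. The initial design also reproduces: exact enumeration of the pooled Z test at 81 per arm gives power 0.901 and alpha 0.0513. The sample-size arithmetic is not at fault.

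**2. When follow-up ends.** End of the 4-week follow-up = removal week + 4.

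| Removed at week | Follow-up ends at week |
|---|---|
| 2 | 6 |
| 9 | 13 |
| 17 | 21 |

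Removal before about week 17 ends this follow-up before the primary endpoint. Chart review cannot supply a research HAI titre. Section 12.6 limits protocol deviations to vaccine administration, so a missed draw would not be recorded as one.

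**3. Size of the bias with no true effect.** Assumptions, since the documents give no removal rate: 74 per arm, true rate 0.333 in both arms, removals in the experimental arm only. Let f be the share removed and q the share of those who would be protected at week 21.

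Rate among those who stay = (0.333 − f·q)/(1 − f); bias = that rate − 0.333.

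Example: f = 0.10, q = 0.20 gives (0.333 − 0.020)/0.90 = 0.348, a bias of +1.5 points. Type I error is by exact enumeration of the two-sided pooled Z test, with round(74(1 − f)) against 74 patients. With no removals it is 5.0%.

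| f | n stayed | q | Rate in stayers | Bias (points) | Type I error |
|---|---|---|---|---|---|
| 0.05 | 70 | 0.20 | 0.340 | +0.7 | 5.4% |
| 0.05 | 70 | 0.333 | 0.333 | 0 | 5.3% |
| 0.05 | 70 | 0.45 | 0.327 | −0.6 | 5.3% |
| 0.10 | 67 | 0.20 | 0.348 | +1.5 | 5.6% |
| 0.10 | 67 | 0.333 | 0.333 | 0 | 5.1% |
| 0.10 | 67 | 0.45 | 0.320 | −1.3 | 5.4% |

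**4. If the planned effect is real.** Suppose stayers reach 0.585 and patients removed after one dose reach 0.333. Stayers then show 0.585 − 0.333 = 25.2 points. All randomised patients would show (1 − f)·0.585 + f·0.333 − 0.333, which is 23.9 points at f = 0.05 and 22.7 at f = 0.10.

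**5. The two meanings of evaluable.** Season 1: 27/50 = 54% have no week-21 assessment. Section 10.3 counts 23. Section 10.2 could admit up to 50, depending on dosing, consent and which visit is the first response assessment. The enrolment plan follows the Section 10.3 meaning: 23 + 125 = 148.

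**The case against.** The strongest reply on removal is that Section 5.3 sets a minimum and does not forbid a week-21 draw, while Sections 1 and 6.5 plan one for all patients. That is fair, but Section 5.4 states a rule (patients will be removed from study), and no section says that sampling continues afterwards. A site following the text could properly stop.

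The arm difference is also narrow. The only trigger confined to one arm is a discretionary example, Section 3.8.1 describes vaccine side effects as generally mild, and a patient removed on that trigger has had one dose, like a control. All of this stands and is why the expected bias is small. The contrast in step 4 is partly a difference in what is being estimated (stayers against all randomised), not purely a bias.

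On the analysis set, the title page and Section 10.3 treat the 27 as not evaluable and replace them with new enrolment, so a complete-case analysis is evidently intended. That also stands. A reader might infer that the plan leaves these patients with no treatment at all, or that Section 10.2 would score them as failures and cost power. Neither is supported: the intent can be read from Section 10.3, and the non-responder rule covers only progression or death. What remains is a conflict between the formal definition and its use.

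**Conclusion.** Both parts hold and should be corrected; confidence is medium. Followed as written, Sections 5.2–5.4 can lose the primary endpoint for removals before about week 17, with some triggers falling only or mainly on the experimental arm. Under no true effect and the assumptions in step 3, the bias is within about 1.5 points in either direction and type I error is at most 5.6%. The bias is zero if removed patients are protected at the control rate.

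A reader might infer that the trial's type I error is seriously inflated or that its result will favour three doses. The documents do not support that. They report no removals by arm, the bias can go either way, and a large inflation would need heavy one-sided removal with nearly all or nearly none of those patients protected.

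The conflict over evaluable does not depend on assumed rates. It affects 27 of the 50 season-1 patients, and it is a gap in the definition, not evidence of an error in the sample size.

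**What to change.** 1. **Sections 5.2–5.4.** Separate stopping study vaccination from leaving the study. In both arms, still collect the scheduled week-21 research blood after vaccination stops, unless consent is withdrawn, the patient cannot be followed, or continued participation is judged not in the patient's best interest. Leave the clinical criteria unchanged, and reconcile these sections with Sections 1 and 6.5.
2. **Section 10.2.** Name week-21 HAI as the response assessment for the primary endpoint, so that Sections 10.2 and 10.3 share one definition of evaluable. State that the 27 season-1 patients who missed week 21 because of COVID19 are missing, not non-responders.
3. **Section 10.4.5.** Report removals and missing week-21 HAI by arm. Add one sensitivity analysis for missing week-21 HAI that uses baseline and week-5 HAI, arm, season and the number of doses actually received, so that a patient stopped after dose 1 is not given a three-dose outcome. Best-case and worst-case bounds are optional.

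The cost is some protocol and SAP wording, a few draws already in the schedule, a little more analysis, and a possible small change in the estimate in either direction.

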5.4 Criteria for removal from study

Patients will be removed from study when any of the criteria listed in [Duration of therapy](#) applies. The reason for study removal and the date the patient was removed must be documented in the appropriate case report form.

5.5 Early stopping rules

If there are any deaths possible, probably, or definitely related to protocol therapy, the trial will be suspended and the [DSMC](#) will provide recommendations for proceeding with the study to the PI.

5.6 Premature termination or suspension of the study

This study may be suspended or prematurely terminated if there is sufficient cause. Written notification, documenting the reason for study suspension or termination, will be provided by the suspending or terminating party to the investigator, funding agency (as applicable) and regulatory authorities. If the study is prematurely terminated or suspended, the PI will promptly inform the IRB and will provide the reason(s) for the termination or suspension.

Circumstances that may warrant termination or suspension include, but are not limited to:

- Determination of unexpected, significant, or unacceptable risk to participants
- Demonstration of efficacy that would warrant stopping Insufficient compliance to protocol requirements
- Data that are not sufficiently complete and/or evaluable
- Determination of futility

6. STUDY PROCEDURES & SCHEDULE

6.1 Agent administration

Treatment will be administered on an outpatient basis. Reported adverse events and potential risks of protocol therapy are described in the pharmaceutical section.

No investigational or commercial agents or therapies other than those described in this protocol may be administered with the intent to vaccinate the patient for influenza or *S. pneumoniae*.

6.1.1 Experimental arm – Intense Fluzone HD

Fluzone HD vaccine for a total of 3 doses beginning at the time of enrollment

6.1.2 Control arm – Single Fluzone HD

Fluzone HD vaccine once at the time of enrollment for a total of 1 dose.

6.2 Definition of dose-limiting toxicity

N/A

6.3 Standard of care study procedures

See [Standard of care and research interventions](#)

6.4 Research specific procedures

See [Standard of care and research interventions](#)

6.5 Schedule of events

Experimental arm

Assessment	Screening + First visit	Week 5 ^a	Week 9 ^a	Week 17 ^a	Week 21 ^a
Signed informed consent	X				
Vital signs	X				
CBC/d/p ^d	X				
CRP, Serum IG's, LDH	X				
Myeloma proteins ^e	X				X
Blood for research ^f	40 mL	40 mL			40 mL
Fluzone HD	X		X	X	
Prevnar (PCV13)		X			
Record grade \geq 2 adverse events ^g	X		X	X	
Influenza-like illness update ^b		X	X	X	X
PFS and OS ^h					X

Control arm

Assessment	Screening + First Visit	Week 5 ^a	Week 9 ^a	Week 17 ^a	Week 21 ^a
Signed informed consent	X				
Vital signs	X				
CBC/d/p ^d	X				
CRP, Serum IG's, LDH	X				
Myeloma proteins ^e	X				X
Blood for research ^f	40 mL	40 mL			40 mL
Fluzone HD	X				
Prevnar (PCV13)		X			
Record grade \geq 2 adverse events ^g	X				
Influenza-like illness update ^b		X	X	X	X
PFS and OS ^h					X

- a. Assessments on these days can be performed within a \pm 5 day window. Subsequent visits (weeks 5, 9, 17, 21) are based on the actual time of Fluzone HD vaccination, not the pneumonia vaccination.
- b. Involves contact between study personnel and the patient regarding influenza-like illness and SAEs. An in-person visit is not required.
- c. All patients (N=148) will have research blood drawn for correlative science. In both arms, blood will be obtained at baseline, week 5, and week 21. The first 20 patients in each group (n=40 total), split evenly between intervention arm (20 experimental, 20 control), had additional blood drawn 1 week after each Fluzone HD dose (week 2 for control arm and weeks 2, 10, and 18 in the experimental arm) – this was completed 17-Nov-2019.
- d. CBC, differential, and platelets will be performed pre-vaccination.
- e. If not done with results available within 30 days of initial vaccination, a modified myeloma disease assessment requested but not required to include SPEP and free light chains if either were measurable per IMWG criteria in the past. Serum IgD or IgE are requested if a monoclonal IgD or IgE were present in the past. For patients with an IgA monoclonal protein, Hevylite IgA can be used to replace serum immunoglobulins and SPEP.
- f. Peripheral blood samples will be obtained and analyzed as described in correlative science section.
- g. Adverse events related to vaccination will be assessed on day of vaccination, and 7 days after each Fluzone HD vaccination (in-person visit for significant adverse events). If patient is unable to be seen in-person, every effort will be made to obtain documentation of patient evaluation, treatment, and resolution of vaccine-related toxicities.
- h. Survival information will be collected through chart review only. An in-person clinic visit is not required.

6.6 Dose levels for protocol-specific drugs

N/A

6.7 Dose interruptions

N/A

6.8 Dose reduction for overlapping toxicities

N/A

7. PHARMACEUTICAL INFORMATION

Complete production and toxicity information for commercial agents can be found in the appropriate FDA approved package insert. Investigator brochure for study agent describes preclinical results and clinical experience to date.

The investigator shall take responsibility for and shall take all steps to maintain appropriate records and ensure appropriate supply, storage, handling, distribution and usage of investigational products in accordance with the protocol and any applicable laws and regulations.

7.1 Fluzone HD

Fluzone HD refers to QIV formulation for 2020-2021 season.

Ingredient	Quantity (per dose)
	Fluzone High-Dose Quadrivalent 0.7 mL Dose
Active Substance: Split influenza virus, inactivated strains:	
A (H1N1)	240 mcg HA total 60 mcg HA
A (H3N2)	60 mcg HA
B (Victoria Lineage)	60 mcg HA
B (Yamagata Lineage)	60 mcg HA
Other:	
Sodium phosphate-buffered isotonic sodium chloride solution	QS [†] to appropriate volume
Formaldehyde	≤140 mcg
Octylphenol ethoxylate	≤350 mcg
Gelatin	None
Preservative	None

*per United States Public Health Service (USPHS) requirement

†Quantity sufficient

Fluzone HD refers to TIV formulation for 2019-2020 influenza season

Ingredient	Quantity (per dose)
	Fluzone High-Dose 0.5 mL Dose
Active Substance: Split influenza virus, inactivated strains^a:	180 mcg HA total
A (H1N1)	60 mcg HA
A (H3N2)	60 mcg HA
B	60 mcg HA
Other:	
Sodium phosphate-buffered isotonic sodium chloride solution	QS ^b to appropriate volume
Formaldehyde	≤ 100 mcg
Octylphenol ethoxylate	≤ 250 mcg
Gelatin	None
Preservative	None

7.1.1 Formulation, appearance, packaging, and labeling

Fluzone HD (TIV) [2019-2020] is supplied as a single-dose, prefilled syringe, without needle, 0.5 mL, in a package of 10.

Fluzone HD Quadrivalent (QIV) [2020-2021] is supplied as a single-dose, prefilled syringe, without needle, 0.7 mL, in a package of 10.

Clinical supplies will be affixed with a clinical label in accordance with regulatory requirements.

7.1.2 Product storage and stability

Fluzone HD will be stored at 2-8°C

The temperature of the storage unit must be recorded daily (excluding non-business days and holidays as applicable), monitored during the duration of the trial per the sites' standard operating procedures, and documentation will be maintained. If the temperature fluctuates outside of the required range, the affected study product(s) must be quarantined at the correct storage temperature and labeled as 'Do Not Use' (until further notice). The pharmacist must alert the site principal investigator and study coordinator, if the temperature fluctuates outside of the required range. In the event the temperature fluctuates outside of the required range, including accidental deep-freezing or disruption of the cold chain, the affected study product(s) must not be administered. Based on the information collected, the manufacturer will determine whether the affected study product(s) can be used. If it cannot be used, the site will receive specific instructions on how to return the affected study product(s) to the manufacturer or destroy it on site.

